8.7.5 Exploratory Endpoint Analysis

The mean change in Acne-Qol domain scores from Baseline to Week 12 will be summarized using descriptive statistics.

Domain scores will be calculated as follows:

1. Code each response. Responses are numbered starting with 0 in ascending order.
 - For questions 1-14 and 18-19:
 - Extremely=0, Very Much=1, Quite A Bit=2, A Good Bit=3, Somewhat=4, A Little Bit=5, Not At All=6
 - For questions 15-17:
 - 0=Extensive, 1=A Whole Lot, 2=A Lot, 3=A Moderate Amount, 4=Some, 5=Very Few, 6=None

2. Check for missing values and impute as follows:
 - Within each domain, a minimum number of responses is required in order to score the domain. At least 3 items must be answered within each domain in order to calculate the domain scores. If the minimum number of items have been answered but 1-2 questions have missing responses, calculate the mean value within the domain for the answered items and replace missing values with the mean value.
3. Calculate overall domain scores for each domain by summing the coded responses to each question in the domain.
 - Domains will be calculated as follows:
 - Self-Perception domain calculated from questions 1, 2, 3, 6, and 10.
 - Role-Emotional domain calculated from questions 4, 5, 7, 8, and 9.
 - Role-Social domain calculated from questions 11, 12, 13, and 14.
 - Acne Symptoms domain calculated from questions 15, 16, 17, 18, and 19.

8.8 Safety Evaluation

8.8.1 Extent of Exposure

The extent of exposure to study drug in each treatment group will be summarized by total number of days of exposure, total number of applications, number of missed applications and number and percentage of subjects who are compliant. A subject will be considered compliant with the dosing regimen if the subject applied 80% to 120% of the expected number of applications and did not miss more than 5 consecutive applications while enrolled in the study.

Days of exposure = Date of last study application – Date of first study application + 1

The total number of applications taken is as follows:

(Date of Last Application – Date of First Application + 1) – (Number of Days marked as missed applications on the CRF) + (Number of extra applications marked on the CRF)

If a subject did apply medication on the last day, the total number of applications expected is as follows:

Date Subject End Participation – Date of Baseline +1.

If the total number of applications exceeds 89 then it will be set to 89.

If a subject did not apply medication on the last day, the total number of applications expected is as follows:

Date Subject End Participation - Date of Baseline

If the total number of applications exceeds 88 then it will be set to 88.

Compliance will be calculated as a percentage as 100 times the total number of applications taken from the first application until Week 12 divided by the total number of applications expected from first application until Week 12. Subjects who discontinue study medication before Week 12 will be considered to be 0% compliant for the number of days from discontinuing study medication until Week 12.

Compliance will not be calculated for subjects who are lost to follow-up or subjects who have unknown first or last application dates.

8.8.2 Adverse Events (AEs)

All AEs occurring during the study will be recorded and classified on the basis of MedDRA terminology. Descriptions of AEs will include the date of onset, the date the AE ended, the severity of the AE, the relationship to study product, the action taken regarding study product usage, the action taken to treat the AE, and the outcome. All reported TEAEs will be summarized by the number of patients reporting AEs, system organ class, severity, seriousness, and relationship to study product. TEAEs are those AEs with an onset on or after the date of the first study product application; if the AE is not indicated as prior to first application on the CRF then it will be considered a TEAE.

AEs will be summarized by treatment group and severity. Each patient will be counted only once within a system organ class or a preferred term by using the AEs with the highest severity within each category.

AEs will be summarized by treatment group and relationship to study product. Each patient will be counted only once within a system organ class or a preferred term by using the AEs with the greatest relationship within each category.

If relationship to study drug is reported as definitely, probably, or possible, then this is defined as related. If relationship to study drug is reported as unlikely or not related, then this is defined as unrelated.

Comparisons among treatment groups will be made by tabulating the frequency of patients with one or more AEs (classified into MedDRA terms) during the study. The Fisher's Exact test will

be used to compare the proportion of patients in each treatment group who report any AE at a significance level of 0.05. The specific system organ classes and preferred terms analyzed will be those that are reported by at least one percent of the patients in any treatment group.

All information pertaining to AEs noted during the study will be listed by patient, detailing verbatim given by the investigator, preferred term, system organ class, start date, stop date, severity, actions taken, and drug relatedness. The AE onset will also be shown relative (in number of days) to the day of initial application of the randomized study product.

Serious adverse events (SAEs) will be tabulated by patient within treatment groups.

In addition, a list of patients who discontinued from the study and a list of patients who experienced SAEs will also be provided.

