17.6 Adverse Events

All AEs occurring during the study will be recorded and classified on the basis of MedDRA terminology. Descriptions of AEs will include the date of onset, the date the AE ended (if applicable), the severity of the AE, the relationship to study product, the action taken regarding study product usage, the action taken to treat the AE, and the outcome. All reported TEAEs will be summarized by the number of Patients reporting AEs, system organ class, severity, seriousness, and relationship to study product. TEAEs are those AEs with an onset on or after the date of the first study product application.

AEs will be summarized by treatment group and severity. Each Patient will be counted only once within a system organ class or a preferred term by using the AEs with the highest severity within each category.

AEs will be summarized by treatment group and relationship to study product. Each Patient will be counted only once within a system organ class or a preferred term by using the AEs with the greatest relationship within each category.

Comparisons among treatment groups will be made by tabulating the frequency of Patients with one or more AEs (classified into MedDRA terms) during the study. The Fisher's Exact test will be used to compare the proportion of Patients in each treatment group who report any AE at a significance level of 0.05. The specific system organ classes and preferred terms analyzed will be those that are reported by at least one percent of the Patients in any treatment group.

All information pertaining to AEs noted during the study will be listed by Patient, detailing verbatim given by the Investigator, preferred term, system organ class, start date, stop date, severity, actions taken, and study product relatedness. The AE onset will also be shown relative (in number of days) to the day of initial dose of the randomized study product.

SAEs will be tabulated by Patient within treatment groups.

In addition, a list of Patients who discontinued from the study and a list of Patients who experienced SAEs will also be provided.

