5. STUDY OBJECTIVES

5.1 Primary Objectives

The primary objectives of this pivotal study are:

- To assess the efficacy of S6G5T-3 compared to its Vehicle when applied once daily for 12 weeks in Patients with acne vulgaris.

- To assess the safety of S6G5T-3 when applied once daily for 12 weeks in Patients with acne vulgaris.

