6.1.2 Method of Assigning Subjects to Treatment Groups

It is planned that approximately 420 Patients, who meet the inclusion/exclusion criteria, will be enrolled in this study at up to 31 U.S. study sites. Patients will be at least 9 years of age and older, of either gender.

The study products will be administered in a double-blinded fashion (i.e., the treatment assignment will not be known to the Patient or to study personnel including Sol-Gel and its representatives). Patients will be instructed not to discuss the study product with the study personnel. Patients will be randomly assigned, in a 2:1 ratio, as follows:

- E-BPO/E-ATRA 3%/0.1% Cream (Product S6G5T-3) (280 Patients)
- Vehicle Cream (Product S6G5T-8) (140 Patients)

Each Patient who signs an informed consent, meets inclusion/exclusion criteria, and successfully completes the screening procedures will be enrolled in the study. The Patient randomization schedule will be a permuted block design stratified by investigational site. Blocks will be composed of 3 treatment assignments in a ratio of 2:1 study product and vehicle respectively. Complete blocks from the randomization schedule will be allocated to investigational sites as they randomize Patients. Patients will be randomized through the IWRS and assigned a unique randomization ID assigning treatment group. The study product supplies will be packed in kits containing 4-pumps and will be numbered in a scrambled randomized method. The kits will be dispensed by the IWRS according to the Baseline assigned randomized treatment group.

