8. STATISTICAL AND ANALYTICAL PLANS

8.1 General Methodology

All statistical processing will be performed using SAS® version 9.3 or later unless otherwise stated. Statistical significance will be based on two-tailed tests of the null hypothesis resulting in p-values of 0.05 or less.

The primary method of handling missing efficacy data will be based on estimation using the method of Markov Chain Monte Carlo (MCMC) imputation. The estimation will be done for each treatment group separately so that the pattern of missingness for one group does not influence the estimation of missing data for another group. Groups of complete datasets following the estimation will be concatenated to form analysis datasets for the comparative

analyses and subsequent imputation result inference with SAS PROC MIANALYZE. Descriptive statistics will also be derived from the multiply imputed datasets.

Sensitivity analyses for the primary efficacy endpoints will use 3 methods. For the lesion count endpoint, the first method will use a repeated measures analysis of covariance (ANCOVA), with treatment, analysis center, visit (i.e., Week 2, Week 4 and Week 8), and treatment group by visit interaction as independent factors and a covariate of Baseline. In this analysis, data from all post-baseline visits will be included with no imputation for missing data.

The second sensitivity analyses will use the model based multiple imputation method to impute missing data for the absolute change at Week 12.

The third sensitivity analysis will involve a tipping point analysis.

Similar methods for the dichotomized IGA will involve a repeated measures logistic regression model and a model based multiple imputation and tipping point analysis.

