Table 14.3.1.2.1: Summary of Treatment-Emergent Adverse Event Characteristics
(Safety Population)
(Page 2 of 2)

	E-BPO/E-ATRA 3%/0.1% Cream (N=xxx)	Vehicle Cream (N=xxx)
By Maximum Severity		
Severe	xx (xx.x%)	xx (xx.x%)
Moderate	xx (xx.x%)	xx (xx.x%)
Mild	xx (xx.x%)	xx (xx.x%)
By Strongest Relationship to Study Drug		
Related	xx (xx.x%)	xx (xx.x%)
Not Related	xx (xx.x%)	xx (xx.x%)
Maximum Severity within Relationship to Study Drug		
Related		
Severe	xx (xx.x%)	xx (xx.x%)
Moderate	xx (xx.x%)	xx (xx.x%)
Mild	xx (xx.x%)	xx (xx.x%)
Not Related		
Severe	xx (xx.x%)	xx (xx.x%)
Moderate	xx (xx.x%)	xx (xx.x%)
Mild	xx (xx.x%)	xx (xx.x%)

Note: Treatment-emergent adverse events are those events that were not indicated as occurring prior to first application.
Related defined as “Definitely”, “Probably”, or “Possible”. Not Related defined as “Unlikely” or “Not related”.

SOURCE: USERNAME/SPONSOR/PROJECT/JOBNAME (DATE, TIME)

Table 14.3.1.2.2: Summary of Treatment-Emergent Adverse Events by MedDRA System Organ Class and Preferred Term
(Safety Population)
(Page 1 of x)

System Organ Class ^a Preferred Term	E-BPO/E-ATRA 3%/0.1% Cream (N=xxx)	Vehicle Cream (N=xxx)	P-Value ^b
XXXXXXXXXXXXXXXXXXXXXXXXXXXX	xx (xx.x%)	xx (xx.x%)	x.xxx
XXXXXXXXXXXXXXXXXXXXXXXXXXXX	xx (xx.x%)	xx (xx.x%)	x.xxx

^a Counts reflect numbers of subjects reporting one or more adverse events that map to MedDRA. At each level of summarization (System Organ Class or Preferred Term) subjects are counted once.

^b P-value for the difference between treatment groups from a Fisher’s Exact test. The specific system organ classes and preferred terms analyzed will be those that are reported by at least one percent of the patients in any treatment group.

Note: MedDRA Version 21.0

Treatment-emergent adverse events are those events that were not indicated as occurring prior to first application.

SOURCE: USERNAME\SPONSOR\PROJECT\JOBNAME (DATE, TIME)

Table 14.3.1.2.3: Summary of Treatment-Emergent Adverse Events by Severity
(Safety Population)
(Page 1 of x)

System Organ Class ^a Preferred Term	Severity	E-BPO/E-ATRA 3%/0.1% Cream (N=xxx)	Vehicle Cream (N=xxx)
XXXXXXXXXXXXXXXXXXXXXXXXXXXX	Severe	xx (xx.x%)	xx (xx.x%)
	Moderate	xx (xx.x%)	xx (xx.x%)
	Mild	xx (xx.x%)	xx (xx.x%)
XXXXXXXXXXXXXXXXXXXXXXXXXXXX	Severe	xx (xx.x%)	xx (xx.x%)
	Moderate	xx (xx.x%)	xx (xx.x%)
	Mild	xx (xx.x%)	xx (xx.x%)

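### Adverse events are compared by an unadjusted Fisher p-value per term, with no risk difference or interval to show how large an excess over vehicle remains possible

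*SAP*

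**What the plan says.** SAP 5.1 lists safety among the primary objectives: "To assess the safety of S6G5T-3 when applied once daily for 12 weeks in Patients with acne vulgaris". That sentence names no comparator. The comparison with vehicle comes from the separate safety objective in SAP 5.4, which covers the nature, severity and frequency of adverse events (AEs) and local tolerability.

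For AEs, SAP 8.8.2 plans by-arm frequency tables and adds that Fisher's exact test is to "be used to compare the proportion of patients in each treatment group who report any AE at a significance level of 0.05". Protocol 17.6 has the same rule: "to compare the proportion of Patients in each treatment group who report any AE at a significance level of 0.05". The test reaches below the any-AE level, and one entry rule governs classes and terms alike: the "preferred terms analyzed will be those that are reported by at least one percent of the patients in any treatment group". The general rule in SAP 8.1 makes it two-sided: "Statistical significance will be based on two-tailed tests of the null hypothesis resulting in p-values of 0.05 or less".

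The shells for Table 14.3.1.2.2 (treatment-emergent AEs, TEAEs) and Table 14.3.1.3.2 (serious TEAEs) show n (%) per arm and one further column, footnoted "P-value for the difference between treatment groups from a" Fisher's exact test. Neither shell, nor the text, has a risk difference, a confidence interval or a multiplicity rule for AEs. Table 14.3.1.2.1, which holds the any-TEAE row, has no comparison column at all. The sample size sections (Protocol 17.7, SAP 9) state power for efficacy only.

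**The concern.** The comparative safety objective asks how AE frequency on active treatment differs from vehicle. The only inferential answer planned is whether each p-value falls at or below 0.05. In a trial sized for efficacy, such a test can be non-significant because there is no excess, or because the trial could not show one. The p-value alone does not separate the two.

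At stake is the wording of the safety conclusion. A column of non-significant p-values is easily summarised as no difference between arms, while an excess of several per hundred may still be compatible with the counts. Testing many terms without adjustment can also produce the occasional significant term by chance, which a bare p-value does not help the reader weigh.

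**Working it through.** **Inputs from the documents.** 280 active and 140 vehicle patients (SAP 6.1.2). Fisher's exact test, two-sided, 0.05 (SAP 8.8.2 and 8.1). Entry to testing at 1% of either arm: 0.01 × 280 = 2.8, so 3 active cases; 0.01 × 140 = 1.4, so 2 vehicle cases.

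**The plan's own figure.** No power is stated for safety. The largest efficacy calculation, which drives the total, is inflammatory lesions: difference 16.7 − 12.2 = 4.5, SD 10.0, 2:1 allocation, 99% power. Vehicle n = (1.960 + 2.326)² × 10² × (1 + 1/2) / 4.5² = 136.1, so 137, with 274 active. This matches SAP 9.

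**Drug-only terms.** With x active cases and no vehicle case, the one-sided Fisher p-value is C(280, x) / C(420, x). The two-sided value adds the tables in the other tail that are no more probable.

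| Active cases (of 280) | Rate | Two-sided p |
|---|---|---|
| 3 | 1.07% | 0.554 |
| 4 | 1.43% | 0.306 |
| 5 | 1.79% | 0.174 |
| 6 | 2.14% | 0.185 |
| 7 | 2.50% | 0.101 |
| 8 | 2.86% | 0.056 |
| 9 | 3.21% | 0.033 |

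Drug-only terms with 3 to 8 cases are therefore tested but cannot be significant. With 1, 2 or 3 vehicle cases, 13, 16 or 20 active cases are needed. The safety population may be smaller than planned: 9 still holds at each smaller 2:1 size checked, down to 238/119, but becomes 10 at 280/130. In the other direction, 3/140 on vehicle against 0/280 on active gives p=0.037, a consequence of 2:1 allocation.

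**Power.** Sum Bin(i; 280, p₁) × Bin(j; 140, p₀) over all tables with i/280 > j/140 and Fisher p ≤ 0.05. The documents give no background rate and no relevant excess, so these rates are assumptions chosen to span a range.

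| Active vs vehicle | Power |
|---|---|
| 3% vs 0 | 46% |
| 5% vs 0 | 94% |
| 3% vs 1% | 15% |
| 5% vs 1% | 54% |
| 8% vs 1% | 92% |
| 10% vs 5% | 39% |
| 15% vs 5% | 89% |

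**What an interval would show.** Take 8/280 vs 0/140. Difference: 8/280 − 0 = 2.86%. Wilson limits are 1.45% to 5.54% for 8/280 and 0 to 2.67% for 0/140. Newcombe lower limit: 2.86 − √[(2.86 − 1.45)² + 2.67²] = −0.2%. Upper limit: 2.86 + √[(5.54 − 2.86)² + 0²] = 5.5%. The planned table would print only p=0.056 beside the counts; the interval shows that an excess of about 5 per 100 is not ruled out.

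**Multiplicity.** The test is conservative for rare terms (actual two-sided error 2.3% when both true rates are 1%, 3.9% when both are 5%). If 10 to 20 independent terms each carried the full 5%, the chance of at least one false positive would be 1 − 0.95¹⁰ = 40% to 1 − 0.95²⁰ = 64%. The number of terms is an assumption, and this is an upper figure.

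**The case against.** The plan is not blind to between-arm differences. AE counts and percentages appear for both arms, so a reader can subtract. Severity, relationship, serious events, discontinuations, cutaneous signs, local tolerability, vital signs, physical findings and patient-rated side effects are all tabulated by arm, and Protocol 17.5 adds graphs of means by week. It would be wrong to infer that Fisher's test is the only yardstick for safety; it is the only inferential one.

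A reader might also infer that the test misses most AE excesses that matter. The documents do not support that. They define no relevant excess, and the power table runs from 15% to 94%. Nor do they give a distribution of AE counts from which to say that most tested rows cannot reach significance; that holds only for particular counts.

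Application-site terms look like the weak spot, because Protocol 14.1 and 14.2 record scale-rated reactions as AEs only when they lead to interruption, withdrawal or new medication. But the same signs and symptoms are scored at Baseline and every later visit whatever their AE status. The SAP's Phase 2 summary also lists application-site dryness, exfoliation and pain among events reaching 5% in some arm. Low AE rates for these terms are possible, not established.

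Finally, the interval leads to the same significance calls as Fisher in the tables checked: it includes zero at 8 vs 0 and excludes it at 9 vs 0; it includes zero at 12 vs 1 and excludes it at 13 vs 1; and it excludes zero for 3/140 on vehicle against none on active. It cures neither the 9-case threshold nor the 2:1 asymmetry. All of this stands. What it leaves untouched is that subtracting two percentages gives no upper limit.

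**Conclusion.** The point holds as a shortfall in how the safety comparison is estimated and reported. The plan attaches a 0.05 test to each AE term and gives no measure of how large an excess over vehicle remains compatible with the data. The thresholds are exact for 280 vs 140. The power figures depend on assumed rates: low for small to moderate excesses, good for large ones.

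Two further readings should be resisted. Neither document says that p>0.05 means no excess, and no safety decision rule hangs on the p-value; the risk lies in later interpretation. And although safety is listed as a primary objective, it is not a co-primary endpoint with a hypothesis to be tested; the comparison with vehicle belongs to SAP 5.4. Nothing here affects the efficacy analysis or the sample size.

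**What to change.** In SAP 8.8.2 and Tables 14.3.1.2.2 and 14.3.1.3.2, and for the any-TEAE row of Table 14.3.1.2.1:

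- Add the risk difference, active minus vehicle, with a 95% confidence interval (Newcombe or Miettinen-Nurminen, named in advance).
- Keep the Fisher p-values beside it, labelled descriptive and unadjusted for multiplicity.
- State that safety conclusions rest on the estimate and its upper limit, and that p>0.05 will not be read as absence of excess risk.

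SAP section 2 gives the SAP precedence over the protocol where they differ, and this does not touch the primary endpoint analysis, so the change can be listed in SAP section 10. It should be made before unblinding.

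The cost is some SAP wording and extra columns in three tables, computed from counts already planned; no new data or patients are needed. The downside is busier tables and visibly wide intervals for uncommon terms.

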8.8.1 Clinical Laboratory Evaluation

Urine pregnancy test results will be presented in a by-subject listing.

8.8.1 Other Observations Related to Safety

8.8.1.1 Cutaneous Safety Assessments

Descriptive statistics by treatment group and visit will be provided for pigmentation, erythema, dryness, and scaling.

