
Primary Efficacy Endpoints:
	
 • Proportion of Patients with an assessment of clear or almost clear and with at least a 2-grade improvement in IGA from baseline at Week 12. • Absolute change from Baseline in lesion count on the face at Week 12 (separately for inflammatory and non-inflammatory lesions).

Secondary Efficacy Endpoints:
	
The secondary efficacy endpoints will be the following:
 
 • Percent change from Baseline, in non-inflammatory lesion count at Week 12. • Percent change from Baseline, in inflammatory lesion count at Week 12. • Proportion of Patients in the E-BPO/E-ATRA cream arm compared to vehicle control achieving at least a 4-point reduction on Item 1 (pimples) of the PRE-FACE from Baseline to Week 12. • Proportion of Patients in the E-BPO/E-ATRA Cream arm compared to vehicle control achieving at least a 4-point reduction on Item 5 (embarrassment) of the PRE-FACE from Baseline to Week 12. • Absolute change from Baseline, in non-inflammatory lesion count at Week 8 • Absolute change from Baseline, in inflammatory lesion count at Week 8. • Absolute change from Baseline, in non-inflammatory lesion count at Week 4. • Absolute change from Baseline, in inflammatory lesion count at Week 4.

Supportive Efficacy Endpoints:
	
 • Proportion of Patients with an assessment of clear or almost clear and with at least a 2-grade improvement from Baseline in IGA, at Weeks 2, 4 and 8. • Absolute change from Baseline in inflammatory and non-inflammatory lesion counts from Baseline to weeks 2, 4 and 8. • PRE-FACE ASD: Mean absolute change in PRE-FACE ASD scores from Baseline to Weeks 2, 4, and 8. • PRE-FACE AID: Mean absolute change in PRE-FACE AID scores from Baseline to Weeks 2, 4, and 8. • Proportion of Patients in treatment relative to control who report at least “minimally improved” as measured by the PGI-C at Week 12. • Patient Global Impress of Symptom Severity (PGI-S) at Week 12. • Patient Global Impression of Treatment Satisfaction (PGI-TS) at Week 12.

Safety Endpoints:
	
 • Adverse events (AEs), including serious adverse events (SAEs) occurring at any time during the trial. • Investigator Cutaneous Safety Assessment and Local Tolerability Assessments score at any time during the trial.

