- Proportion of Patients in treatment relative to control who report at least “minimally improved” as measured by the PGI-C at Week 12.
- Patient Global Impress of Symptom Severity (PGI-S) at Week 12.

- Patient Global Impression of Treatment Satisfaction (PGI-TS) at Week 12.

The safety objectives of this pivotal study are:

To determine the nature, severity and frequency of the AEs rate and the local cutaneous reaction and tolerability of Products S6G5T-3 compared to the vehicle.

The safety endpoints to be assessed include the following:

- The frequency of both local and systemic AEs
- Investigator Cutaneous Reaction (erythema, dryness, pigmentation and scaling) and Local Tolerability Assessment (itching burning and stinging) at Baseline and at all study visits.

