14.1 Cutaneous Reactions Assessments

The evaluator will assess local application site cutaneous reactions by rating the erythema, dryness, pigmentation and scaling at each study visits except Screening visit. The evaluator will determine the score for each of these variables by direct evaluation. The following definitions of terms will be applied to these evaluations.

Cutaneous Signs Evaluation will include assessments of erythema, scaling, dryness and pigmentation based on the following 4-point scale shown in table 3 below.

Table 3: Assessments of erythema, scaling, dryness and pigmentation

	Score	Rating	Definition
Erythema	0	None	No erythema
	1	Mild	Slight pinkness present
	2	Moderate	Definite redness, easily recognized
	3	Severe	Intense redness
Scaling	0	None	No scaling
	1	Mild	Barely perceptible shedding, noticeable only on light scratching or rubbing
	2	Moderate	Obvious but not profuse shedding
	3	Severe	Heavy scale production
Pigmentation	0	None	No disturbance of pigmentation
	1	Mild	Barely perceptible pigment change
	2	Moderate	Markedly darker or lighter
	3	Severe	Complete de-pigmentation or severe hyperpigmentation
Dryness	0	None	No dryness
	1	Mild	Slight but define roughness
	2	Moderate	Moderate roughness
	3	Severe	Marked roughness

Application site reactions (erythema, scaling, dryness and pigmentation) are not to be recorded as AEs unless they result in either:

- The temporary discontinuation of the study product.
- The discontinuation of the Patient from the study.
- The use of a new concomitant medication in order to treat this event.

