8.1.5 Handling of Dropouts or Missing Data

Missing data for the ITT population will be estimated by multiple imputation and subsequently analyzed. Missing lesion count and IGA data will be derived for the analysis using the method of Markov Chain Monte Carlo (MCMC) multiple imputation. The pattern of missing observations

in each treatment group cannot influence the missing value estimation in the other group because the imputation will be conducted independently for each treatment group.

Last observation carried forward (LOCF) will be used to impute missing data for the efficacy analyses using the Per Protocol (PP) population.

Patients that discontinue from the study due to an AE related to study treatment or documented lack of treatment effect will be included in the PP population. Data for these subjects will not be imputed by multiple imputation or LOCF but rather their data will be imputed with values consistent with their status as treatment failures. For these subjects, values for lesion count and IGA will be imputed such that change from Baseline is zero, meaning the values will be set to the Baseline value. This imputation will be done after the data for all subjects has been through the MI process.

Incomplete start and end dates for medications will be imputed. Other safety data will not be imputed and will be summarized on an observed case basis.

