8.8.1.2 Local Tolerability Assessments

Descriptive statistics by treatment group and visit will be provided for itching, burning and stinging.

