 Role-Emotional domain calculated from questions 4, 5, 7, 8, and 9.
 Role-Social domain calculated from questions 11, 12, 13, and 14.
 Acne Symptoms domain calculated from questions 15, 16, 17, 18, and 19.

SOURCE: USERNAME\SPONSOR\PROJECT\JOBNAME (DATE,TIME)

Table 14.2.17.1: Summary of Acne-QoL Questionnaire Responses at Baseline and Week 12
(Intent-to-Treat Population)
(Page 4 of 4)

Acne Symptoms Domain	E-BPO/E-ATRA 3%/0.1% Cream (N=xxx)	Vehicle Cream (N=xxx)
Baseline		
n	xx	xx
Mean	xx.x	xx.x
SD	xx.xx	xx.xx
Median	xx.x	xx.x
Min. to Max.	xx to xx	xx to xx
Week 12		
n	xx	xx
Mean	xx.x	xx.x
SD	xx.xx	xx.xx
Median	xx.x	xx.x
Min. to Max.	xx to xx	xx to xx
Absolute Change from Baseline		
n	xx	xx
Mean	xx.x	xx.x
SD	xx.xx	xx.xx
Median	xx.x	xx.x
Min. to Max.	xx to xx	xx to xx

Note: No imputation of missing values. Change calculated as Week 12 – Baseline. Negative values represent decrease from Baseline.
 Self-Perception domain calculated from the questions 1, 2, 3, 6, and 10.
 Role-Emotional domain calculated from questions 4, 5, 7, 8, and 9.
 Role-Social domain calculated from questions 11, 12, 13, and 14.
 Acne Symptoms domain calculated from questions 15, 16, 17, 18, and 19.

SOURCE: USERNAME\SPONSOR\PROJECT\JOBNAME (DATE,TIME)

Table 14.3.0.1: Summary of Extent of Exposure
(Safety Population)

	E-BPO/E-ATRA 3%/0.1% Cream (N=xxx)	Vehicle Cream (N=xxx)
Total Number of Days of Exposure		
n	xx	xx
Mean	xx.x	xx.x
SD	xx.xx	xx.xx
Median	xx.x	xx.x
Min. to Max.	xx to xx	xx to xx
Total Number of Applications		
n	xx	xx
Mean	xx.x	xx.x
SD	xx.xx	xx.xx
Median	xx.x	xx.x
Min. to Max.	xx to xx	xx to xx
Total Number of Missed Applications		
n	xx	xx
Mean	xx.x	xx.x
SD	xx.xx	xx.xx
Median	xx.x	xx.x
Min. to Max.	xx to xx	xx to xx
Compliant^a		
n	xx	xx
Yes	xx (xx.x%)	xx (xx.x%)
No	xx (xx.x%)	xx (xx.x%)

^a A subject was considered compliant with the dosing regimen if the subject applied 80-120% of the expected number of applications and did not miss more than 5 consecutive applications while enrolled in the study.

SOURCE: USERNAME\SPONSOR\PROJECT\JOBNAME (DATE,TIME)

Table 14.3.1.1: Summary of Cutaneous Signs and Local Tolerability at Each Evaluation
(Safety Population)
(Page 1 of 14)

Erythema	E-BPO/E-ATRA 3%/0.1% Cream (N=xxx)	Vehicle Cream (N=xxx)
Baseline		
n	xx	xx
0 – None	xx (xx.x%)	xx (xx.x%)
1 – Mild	xx (xx.x%)	xx (xx.x%)
2 – Moderate	xx (xx.x%)	xx (xx.x%)
3 – Severe	xx (xx.x%)	xx (xx.x%)
Week 2		
n	xx	xx
0 – None	xx (xx.x%)	xx (xx.x%)
1 – Mild	xx (xx.x%)	xx (xx.x%)

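### Local skin reactions are summarised visit by visit only, so no output gives the per-patient any-time frequency, worst grade or worsening from Baseline

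*SAP*

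**What the plan says.** The protocol words the endpoint in more than one way. The synopsis lists, among the safety endpoints, "Investigator Cutaneous Safety Assessment and Local Tolerability Assessments score at any time during the trial". Section 7 instead lists the cutaneous reactions and "Local Tolerability Assessment (itching burning and stinging) at Baseline and at all study visits", under an objective that covers the "nature, severity and frequency of the AEs rate and the local cutaneous reaction and tolerability" compared with vehicle. Protocol 17.5 plans descriptive statistics at Baseline and Weeks 2, 4, 8 and 12, with the frequency and percentage of each grade. SAP 7.2 gives no time frame.

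For the analysis, SAP 8.8.1.1 states: "Descriptive statistics by treatment group and visit will be provided for pigmentation, erythema, dryness, and scaling". SAP 8.8.1.2 states: "Descriptive statistics by treatment group and visit will be provided for itching, burning and stinging". On missing data, SAP 8.1.5 states: "Other safety data will not be imputed and will be summarized on an observed case basis". The one planned summary of these scores is "Table 14.3.1.1: Summary of Cutaneous Signs and Local Tolerability at Each Evaluation". Its shell gives n and n (%) for grades 0 to 3 at Baseline and the four post-baseline visits.

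Protocol 14.1 says these application site reactions "are not to be recorded as AEs unless they result in either" temporary interruption of the product, discontinuation of the patient, or a new concomitant medication. Protocol 14.2 applies the same rule to itching, burning and stinging.

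**The concern.** An any-time endpoint calls for one result per patient: the worst score after Baseline, or whether the score ever rose above Baseline. A set of separate visit columns does not give that. Mild or moderate irritation may come and go, and the columns cannot show whether the same few patients or many different ones are affected.

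At stake is the description of local tolerability, a main safety question for a topical product of this kind. A reader of the report could not say what share of patients on each arm ever had, for example, moderate burning, or how many were worse than when they started. Later columns also lose patients who have left, so a declining percentage may partly reflect who remains.

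**Working it through.** The documents give no expected irritation rate, dropout rate or precision target for these scores, so there is no planned figure to reproduce. The check compares the planned outputs with the question and then shows, under assumed rates, how far apart the two measures can be.

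**1. What each output delivers.**
- Table 14.3.1.1: grade frequencies per visit, observed cases. It has no any-time row, no worst-grade row and no comparison with Baseline.
- Shift tables: planned for vital signs only (SAP 8.8.1.3, Table 14.3.1.4.2).
- AE tables (SAP 8.8.2): each patient counted once at highest severity over the study, but only for reactions that meet the Protocol 14.1 and 14.2 conditions.
- Listing 16.2.7.1: individual scores, not a summary.
- SAP section 10 (changes in planned analyses): no mention of the any-time endpoint.

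**2. Which scores reach the by-visit table.** Under SAP 8.1.3, early-termination and unscheduled scores are mapped to a visit window. They are left out if they fall before day 8 (unless they serve as Baseline), after day 98, or in a window that already holds a scheduled score. If several fall in one window, only the one closest to the target day is used. Yet Protocol 12.16 names reporting discomfort after using the product as an example of a reason for an unscheduled visit. Scoring at such a visit is at the Investigator's discretion, so the number of scores lost is unknown.

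**3. Any-time frequency from by-visit frequencies.** Assume complete data and the same proportion p with a given reaction at each of the four post-baseline visits. Then:
- lower limit = p (the same patients every time);
- upper limit = min(1, 4p) (different patients every time);
- independence between visits = 1 − (1 − p)^4.

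| p per visit (assumed) | Lower | Independence | Upper |
|---|---|---|---|
| 5% | 5% | 1 − 0.95^4 = 18.5% | 20% |
| 10% | 10% | 1 − 0.90^4 = 34.4% | 40% |
| 20% | 20% | 1 − 0.80^4 = 59.0% | 80% |

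Scores in the same patient are likely to be correlated. Simulating a latent normal variable with equal correlation between visits, p = 10% gives 29.6%, 25.9% and 21.8% ever affected at correlations of 0.3, 0.5 and 0.7.

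**4. Selective withdrawal.** Take the planned 280 active patients. Assume 28 (10%) are irritated at Week 2, irritation persists in those who stay, and nobody else is affected. Assume also that leavers contribute no score to the later visit. If a fraction f of the 28 leave, the later visit shows 28(1 − f)/(280 − 28f):
- f = 25%: 21/273 = 7.7%;
- f = 50%: 14/266 = 5.3%;
- f = 75%: 7/259 = 2.7%.

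The any-time figure stays at 28/280 = 10%.

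**The case against.** The strongest reply is that the SAP does what the protocol's analysis section asks. Protocol 17.5 specifies by-visit frequencies, section 7 names the visits, and SAP section 2 says the SAP prevails where the documents differ. The synopsis line follows a similar one about AEs and may describe only the collection period. This stands as a reason to reconcile the wordings, and it means that the by-visit table is not an error.

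A reader might go further and infer that the frequency of irritation is not estimated at all. The documents do not support that: Table 14.3.1.1 gives the count and percentage of every grade for all seven signs and symptoms, by arm, at every visit.

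Nor can one say that no other output counts affected patients. A reaction that leads to withdrawal, interruption or new medication must be recorded as an AE and is then counted once per patient. Table 14.3.1.2.1 also counts patients who stopped drug or study because of a TEAE, and Table 14.3.1.6 shows by visit how bothered patients were by side effects. The gap concerns reactions without such action, and a per-patient summary of the scores themselves.

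It would also be too strong to say that later columns contain only those who stayed. Scoring is required at early termination, and an exit score on days 8 to 98 can enter one window if no scheduled score is there. The patient is absent after that.

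Finally, the lower limit in step 3 needs complete data. With a shrinking denominator it can fail: 20 of 200 remaining patients at Week 12 is 10%, while 20 of 280 ever affected is 7.1%.

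**Conclusion.** The point holds in a limited form. Nature, grade and by-visit frequency are reported. The per-patient any-time frequency, the worst post-baseline grade and worsening from Baseline are not, and by-visit percentages cannot supply them. With complete data, 10% at each of four visits leaves the any-time figure anywhere from 10% to 40%. All rates here are assumptions, and the actual gap depends on how persistent the reactions are and who withdraws.

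No hypothesis test is affected. The change is still worth making: it answers the synopsis endpoint and the frequency part of the objective. It also parallels a measure that SAP section 4 reports from the Phase 2 study, the proportion of patients whose self-assessed score was higher than at Baseline at least once.

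**What to change.** 1. Reconcile the endpoint wording in the protocol synopsis, Protocol 7 and 17.5, and SAP 7.2.
2. Add to SAP 8.8.1.1 and 8.8.1.2 a table, by arm in the Safety population, for each of erythema, scaling, pigmentation, dryness, itching, burning and stinging. It should give n (%) by worst post-baseline grade, and n (%) with any post-baseline score above the patient's own Baseline.
3. Base it on all post-baseline scores, including every early-termination and unscheduled score. State in SAP 8.1.3 that the visit-window exclusions do not apply to this summary; otherwise the two sections would conflict.
4. Keep Table 14.3.1.1 as it is.

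The cost is one extra descriptive table from data already collected, with no change to trial conduct.
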